2. OBJECTIVES

There is usually only one primary objective, the rest are secondary objectives.

The wording of the objectives should be clear, unambiguous and as specific as possible.

3.1 Primary Objective

The aim of the project is to assess the feasibility of this non-invasive sampling method to monitor CIN2 lesions in order to identify biomarker patterns that are consistent with lesion progression/ regression.

3.2 Secondary Objectives: None

3. STUDY DESIGN

4.1 Summary of Study Design

This is a single-centre, non-randomised, cohort interventional and lab-based study Duration: 12 to 18 months

21/01/2022; Version 4

4.2 Primary and Secondary Endpoints/Outcome Measures

As this is a feasibility study, the primary measure is that of demonstrating initial utility of this approach to non-invasively monitor women with CIN2 lesions and demonstrate biomarker patterns that are consistent with lesion regression or progression.

4.3 Study Participants

4.3.1 Overall Description of Study Participants

Female patients with >moderate dyskaryosis who are between 25 and 35 years of age with histologically confirmed CIN2 in a single quadrant of the cervix

4.3.2 Inclusion Criteria

To enter the study all of the following criteria must be satisfied:

- Participant is willing and able to give informed consent for participation in the study.
- Female, aged between 25 to 35 years
- (1) Diagnosed with CIN2 and have been co-enrolled into the cervical Cell Lifts Study OR

(2) Diagnosed with CIN2 and have been in a conservative management pathway for up to 6 months

4.3.3 Exclusion Criteria

The participant may not enter the study if ANY of the following apply:

- Participant is unable to give consent.
- Pregnant
- HIV/Systemic Immuno-suppression
- Previous contraindication or allergy nail varnish/ nitrocellulose

3.4 Study Procedures

- 1. Written informed consent will be given prior to the patient's initial colposcopy
- 2. During the colposcopy examination, a digital image of the cervix will be taken according to standard practice.
- 3. A filter disk of nitrocellulose (of up to 50mm diameter and marked to indicate the 12 O'clock position) will then be gently pressed onto the surface of the cervix for 10 to 15 seconds prior to it being peeled off and removed for storage. The filter with adherent exfoliated cells will then be fixed (in acetone/methanol, ethanol, or 5% formaldehyde) prior to analysis at the level of cytology or immunostaining or DNA/ RNA analysis as part of the research collaboration between the University of Cambridge and Addenbrookes Hospital.
- 4. The remainder of the colposcopy examination will then follow its standard course, with identification of single quadrant disease and impression of CIN2
- 5. Biopsy of single quadrant disease (to confirm CIN2)
- 6. Up to 4 further f/u visits follow the same format with the notable exception of the absence of a further biopsy until the 12-month final visit

4.4.1 Informed Consent

Informed consent will be given prior to the patient's first colposcopy visit associated with this study. When they attend the clinic, the research team will discuss the study merits and limitations and written consent will be given prior to the participant seeing the colposcopist. Consent will be re-confirmed

verbally at each subsequent follow-up visit (and documented in the patient's notes). Concurrent to this study all patients would also be approached for informed written consent for the larger patch sampling study as currently occurs.

4.4.2 Sample Analysis

For this feasibility study, we envisage that 10 patients will be adequate.

These will be triple stained with a pan E4 antibody to identify areas of virus infection (LSIL), along with p16/MCM to identify cells that are abnormally progressing through the cell cycle (HSIL). Images of the stained cells will be captured using a digital imaging system prior to H+E staining or staining with the Pap stain. The immunostaining and histology images will be compared against the images taken during the colposcopy examination and with the results of the biopsy analysis. For all patients, we will also request sections from the biopsy material in order to better understand how biomarker expression at the epithelial surface (in the cell-lifts) relates to expression of the same biomarkers in the underlying disease and Patch approach.

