The study will involve monitoring patients with our non-invasive technique in conjunction with colposcopy (Fig 3) to assess the feasibility of this method. The main risk to any patient is the risk of progression to CIN3 and worse cancer. However, as the majority of CIN2 patients across the UK are now offered conservative management and as many recent papers have demonstrated lesion regression in >50% of CIN2 cases this risk (over the duration of the study) is extremely low(1–6). Moreover, in order to further minimize this risk, we will follow-up these patients more intensively than the norm (usually conservative management of CIN2 involves 6-month follow-up colposcopy) with 3 monthly colposcopy visits for up to 1 year with the same named colposcopist (to reduce any inter-observer variability) where possible. If a different colposcopist is used, we will aim to mitigate

any increased variability by using and comparing colposcopic photographs taken during each colposcopy visit. This will allow us to ensure that variations in diagnosis are kept to a minimum.

Finally, as we are using biomarkers to identify lesions on the patch, any marker pattern that is suggestive of higher-grade disease will result in the patient having a colposcopic visit together with adequate counselling and biopsies/ treatment as required. We feel that this approach enables us to minimize the already low risk of progression even further thus allowing women to give informed consent in an ethical manner. There are no operceivable risks involved.

Fig 3. Study scheme demonstrating entire patient pathway including patient withdrawal points. Colposcopic photographs will be taken during each colposcopy visit and all histology will be reviewed/compared by histopathologists. A) Pathway for patients who recruited after diagnosis with CIN2, B)) Pathway for patients who recruited from the pre-existing clinical pathway either at 3 month visit (-/+ 2 week) or at the 6 month routine clinical visit (-/+ 2 week).

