6.2 Analysis of Endpoints

Each patient will have their samples probed for evidence of lesions. During the follow-up period we will be observing if these lesions progress or regress with concurrent marker pattern changes i.e. if lesion is of low progression potential, we expect high E4 expression and low p16/MCM expression and vice versa. The final endpoint analysis will look for correlation of these biomarker patterns to the final histology or colposcopy outcome. We expect high E4 expression lesions to regress and vice versa.

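### Nothing requires patch staining to be scored and locked before it is compared with colposcopy and histology, so the main correlation is open to review bias

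*Protocol*

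**What the plan says.** Protocol 4.4.2 (Sample Analysis) is the only section on how a stained patch is analysed. Patches are triple stained for E4, p16 and MCM, and then: "Images of the stained cells will be captured using a digital imaging system prior to H+E staining or staining with the Pap stain". The next sentence is the comparison: "The immunostaining and histology images will be compared against the images taken during the colposcopy examination and with the results of the biopsy analysis". The section adds, for all patients, "we will also request sections from the biopsy material in order to better understand how biomarker expression at the epithelial surface" relates to expression in the underlying disease.

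Protocol 6.2 (Analysis of Endpoints) uses the readings as follows: "The final endpoint analysis will look for correlation of these biomarker patterns to the final histology or colposcopy outcome". The reading is described only as high or low. For lesions of low progression potential, "we expect high E4 expression and low p16/MCM expression and vice versa". The expected result is given in advance: "We expect high E4 expression lesions to regress and vice versa".

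In Background and Rationale, the Fig 3 caption says that "all histology will be reviewed/compared by histopathologists", without saying what else the histopathologists may see. The same section asks for one named colposcopist where possible and for photographs to be compared across visits. Those measures address variation between colposcopists, not the reading of the patch.

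**The concern.** The patch reading is the measurement under test, and colposcopy and histology are what it is tested against. Deciding whether patchy E4 or p16/MCM staining is high or low takes judgement when no scoring rule is given. A reader who already knows where the acetowhite area lies, or how the lesion turned out, can resolve doubtful staining in the direction that 6.2 expects. The same can happen in reverse if the final histology is graded with marker results in view.

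Any correlation would then partly reflect shared information. With about 10 women, a few such readings could produce the pattern that the study sets out to find. Section 6.1 expects a robust analysis from these women, and the Ethics section hopes that the results will inform who is offered conservative or excisional treatment.

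**Working it through.** **No plan figure to reproduce.** Section 6.1 gives 10 patients without a significance level, power or effect size, and this point disputes no figure.

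**Step 1: what the reader could know, patch by patch.**
- *Diagnostic biopsy.* CIN2 in every participant by eligibility (4.3.1, 4.3.2), so knowing it cannot separate women who regress from women who progress.
- *Same-visit colposcopy.* The Synopsis schedules an acetowhite photograph with every patch. The disk is fixed and analysed after the visit (Study Procedures, step 3), so the photograph already exists when the patch is read. Section 6.2 accepts a colposcopy outcome, so part of the reference is available for every patch.
- *Final histology.* Study Procedures, step 6, plans no further biopsy until the 12-month visit. The 12-month patch comes from the same visit as the final biopsy or excision, so its reading can follow the result. A 3-, 6- or 9-month patch read on arrival would normally precede it. A patch scored or re-scored in an end-of-study batch would not.

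**Step 2: could a few readings matter with 10 women?** This is an illustration only. The inputs below are assumptions; none is in the protocol.
- The marker is uninformative: it agrees with the outcome with probability 0.5.
- A share s of discordant readings is pulled to the known outcome.
- Agreement probability is p = 0.5 + 0.5s.
- The number of agreements is binomial (10, p). For s = 0, P(at least 8) = (45 + 10 + 1)/1024 = 5.5%.
- The last column is the chance that a two-sided Fisher test at 0.05 rejects, with 5 women regressing and 5 not.

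| s | p | P(≥8 of 10) | P(≥9 of 10) | Fisher rejects |
|---|---|---|---|---|
| 0 | 0.50 | 5.5% | 1.1% | 2.1% |
| 0.1 | 0.55 | 10.0% | 2.3% | 2.8% |
| 0.2 | 0.60 | 16.7% | 4.6% | 4.8% |
| 0.3 | 0.65 | 26.2% | 8.6% | 8.6% |
| 0.5 | 0.75 | 52.6% | 24.4% | 24.4% |

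A 6:4 split gives the same Fisher column. A 7:3 split gives 1.6%, 2.0%, 3.5%, 6.5% and 18.8%.

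**Step 3: one woman can decide the result.** With a 5:5 split, high E4 in 4 of 5 regressing and 1 of 5 not regressing is 8 of 10 agreements, Fisher p = 0.206. Re-reading one regressing woman as high gives 5 of 5 against 1 of 5, which is 9 of 10 agreements, p = 0.048.

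**The case against.** The strongest reply is that the comparison in 4.4.2 is one that any study relating a marker to a reference must make. A reader might infer from it that staining is graded with the colposcopy and biopsy results in view. The documents do not say so: 4.4.2 sets no order of grading at all. That reply stands, and the point is therefore about what the plan allows, not what it orders.

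A second reply also stands in part. Background and Rationale provides that "any marker pattern that is suggestive of higher-grade disease will result in the patient having a colposcopic visit together with adequate counselling and biopsies/ treatment". This implies that patches are read during follow-up, normally before any final histology exists. But nothing says that those readings are recorded or that they are the ones analysed in 6.2, and they do not remove exposure to same-visit colposcopy. The provision also lets the marker influence when outcome tissue is obtained. That is a separate dependence, which a locked score does not remove.

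Third, a reader might infer that the people who read the patches also stain the biopsy sections, or that histopathologists see patch results. The protocol says only that sections will be requested and histology reviewed. It does not say who stains the sections, and it neither describes nor rules out sight of patch results.

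Fourth, this is a feasibility study. Section 4.2 asks for initial utility and for biomarker patterns, and no agreement statistic is named. This limits how much weight the result will bear. The correlation in 6.2 is still the analysis that would show the patterns.

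Finally, reading order might be set out in a document not shown here. It is a laboratory procedure, though, and 4.4.2 is where this protocol describes that procedure.

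**Conclusion.** The concern holds as a gap in the reading procedure. The protocol allows an undefined high or low reading, with a declared expected direction, to be made after the reader has seen what it will be correlated with. The exposure is limited to same-visit colposcopy findings at any visit, and to the outcome for the 12-month patch and any patch scored or re-scored at the end. It does not arise from baseline histology.

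The size of the bias cannot be estimated from the documents, which give no inter-reader or re-reading figure. The table shows only that a result in about 10 women is sensitive to a small number of swayed readings. It rests on an assumed uninformative marker, pull rate, outcome split, test and 0.05 level. This should be corrected, but it does not undermine the study's feasibility purpose.

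**What to change.** Add a reading sequence to 4.4.2:

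1. Each patch's E4 grade, p16/MCM grade and lesion position (against the 12 o'clock mark on the disk) are entered under study ID and locked before the reader sees that visit's colposcopy images or any follow-up histology.
2. The locked score is the one used in 6.2. Any later re-reading is kept separately.
3. The histopathologist records the final grade before seeing patch results or the study's marker-stained sections.
4. The side-by-side comparison in 4.4.2 follows.

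The cost is a small sequencing burden and a locked column in the existing spreadsheet. It needs no extra reader, sample or visit, and leaves clinical management as it is, including action on patch results during follow-up.

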4.5 Definition of End of Study

The recruitment of new participants will stop when 10 evaluable patients have been recruited to the study or by the end of 2022, whichever is sooner. Evaluability is determined by having at least 3 full datasets (3 different time points). The study will end when the last patient has completed her last follow-up visit. Any participants recruited after the 10th evaluable participant who are still active in the study will be followed -up and included in the final analysis. The total number of participants recruited to the study may therefore be more than 10. All data capture will stop at the end of 2022, regardless of whether the full set of 10 evaluable participants has been accrued.

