1. SYNOPSIS

Study Title	Monitoring of Cervical lesions at Colposcopy using a novel non-invasive technique for monitoring of CIN2 lesions (a pilot/ feasibility study)			
Internal ref. no.	R&D			
Study Design	The is a single-centre, non-randomised, cohort interventional & lab based study			
Study Participants	Women with abnormal cytology attending the colposcopy clinic that have single quadrant disease that is histologically CIN2. The women will be identified from the larger Cervical Cell Lift study (17/SC/0203) or from the pre-existing standard of care conservative management pathway.			
Planned Sample Size	10			
Follow-up duration	From 6 months to 1 year (3 monthly intervals)			
Planned Study Period	12 to 18 months			
Primary Objective	To non-invasively monitor women with CIN2 using a novel non-invasive approach in order to identify biomarker patterns that are consistent with lesion regression/ progression			
Secondary Objectives	None			
Primary Endpoint	As this is a feasibility study, the outcome is considered to be the ability to identify biomarker patterns consistent with lesion regression/ progression			
Secondary Endpoints	-			
Intervention (s)	 If enrolled to the study after CIN2 diagnosis: Primary visit for Colposcopy – CIN2 identified, acetowhite photograph and Patch taken followed by biopsy 3-month visit for Colposcopy – Patch, acetowhite photograph taken and colposcopy done to ensure no change in lesion and comparison with previous photograph of acetowhite change 6-month visit for Colposcopy - Patch, acetowhite photograph taken and colposcopy done to ensure no change in lesion and comparison with previous photograph of acetowhite change 9-month visit for Colposcopy - Patch, acetowhite photograph taken and colposcopy done to ensure no change in lesion and comparison with previous photograph of acetowhite change 9-month visit for Colposcopy - Patch, acetowhite photograph taken and colposcopy done to ensure no change in lesion and comparison with previous photograph of acetowhite change 1-year visit for Colposcopy – Patch, acetowhite photograph taken and either further biopsy or excisional treatment as per colposcopist impression If enrolled to the study from the pre-existing clinical pathway, participants will start the study at either the 3 month visit (-/+ 2 week) or the 6 month routine clinical visit (-/+ 2 week) following CIN2 diagnosis. 			

BACKGROUND AND RATIONALE

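### Recruitment may stay open until the day all data capture closes, so women entering after about 30 June 2022 cannot become evaluable, and the fixed stop conflicts with the follow-up rules in the same section

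*Protocol*

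**What the plan says.** Protocol section 4.5 contains five rules that bear on this point.

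- Recruitment: it closes on reaching ten evaluable women, "or by the end of 2022, whichever is sooner". The calendar date is a backstop to the target of ten.
- Evaluability: "Evaluability is determined by having at least 3 full datasets (3 different time points").
- End of study: "The study will end when the last patient has completed her last follow-up visit".
- Women recruited after the tenth evaluable participant who are still active are to be followed up and analysed.
- Data stop: "All data capture will stop at the end of 2022". This applies even if fewer than ten evaluable women have been reached.

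The Synopsis sets visits three months apart and follow-up of six months to one year. A woman may enter at diagnosis, or from the existing conservative-management pathway at month 3 or month 6 after diagnosis, with a two-week window either side of those entry visits. The one-year visit carries "either further biopsy or excisional treatment as per colposcopist impression". Section 3.4 (Study Procedures) plans no further biopsy before that visit. Section 6.2 relates biomarker patterns to the final outcome, by histology or by colposcopy. Section 6.1 counts only women who complete the full duration of the study. The version stamp in section 4.1 reads "21/01/2022; Version 4".

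**The concern.** Last entry and last data capture have different jobs. They should be separated by at least the follow-up needed to make an entrant usable. Here they share a date. Anyone recruited in the final months gives consent and attends research visits, yet cannot meet the protocol's own definition of an evaluable participant. The Ethics section justifies the more intensive follow-up by what will be learned from it, and that justification is weak for women who cannot be evaluable.

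The second issue is the outcome. The only histology planned after baseline is at 12 months. With about ten women, losing it for one entry route changes the kind of outcome against which the biomarkers are compared.

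The third is internal consistency. For any woman still in follow-up at the end of 2022, a fixed data stop is incompatible with following her up and analysing her, and with a study end defined by the last follow-up visit.

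**Working it through.** The protocol gives no last-entry calculation to reproduce. The planned number of ten is a judgement and plays no part here. The check is calendar arithmetic on the protocol's own schedule.

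**Inputs**
- Data stop: 31 December 2022 (4.5).
- Datasets needed to be evaluable: 3 (4.5).
- Visit spacing: 3 months (Synopsis).
- Visit months after diagnosis: 0, 3, 6, 9, 12 (entry at diagnosis); 3, 6, 9, 12 (month-3 entry); 6, 9, 12 (month-6 entry).
- Version date: 21 January 2022 (4.1).

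**Formulas**
- Time from entry to third dataset = 2 intervals × 3 months = 6 months on every route.
- Last evaluable entry = 31 December 2022 − 6 months = 30 June 2022.
- Last entry that reaches month 12 = 31 December 2022 − (12 − entry month) months.

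| Route | Last entry for 3 datasets | Last entry to reach month 12 |
|---|---|---|
| At diagnosis | 30 Jun 2022 | 31 Dec 2021 |
| Month-3 entry | 30 Jun 2022 | 31 Mar 2022 |
| Month-6 entry | 30 Jun 2022 | 30 Jun 2022 |

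**Datasets captured by 31 December 2022, by entry date**

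| Entry date | At diagnosis | Month-3 entry | Month-6 entry |
|---|---|---|---|
| 21 Jan 2022 | 4 | 4 | 3 |
| 31 Mar 2022 | 4 | 4 | 3 |
| 30 Jun 2022 | 3 | 3 | 3 |
| 1 Jul 2022 | 2 | 2 | 2 |
| 30 Sep 2022 | 2 | 2 | 2 |
| 31 Dec 2022 | 1 | 1 | 1 |

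From 1 July to 31 December 2022 (184 days) recruitment can be open without any entrant becoming evaluable.

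**Entry at diagnosis under this version.** 21 January 2022 + 12 months = 21 January 2023. With the final visit two weeks early, it is 7 January 2023. Both fall after the stop.

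**Sensitivity to a visit window.** The two-week window is stated only for pathway entry. If it is assumed to apply to follow-up visits too, each cut-off moves 14 days later. The evaluability cut-off becomes 14 July 2022, and the at-diagnosis cut-off for month 12 becomes 14 January 2022, still before the version date. For pathway entrants, a two-week-late entry combined with a two-week-early third visit would give 28 July 2022. No entry window is stated for the diagnosis route.

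**If recruitment to 31 December 2022 were kept.** The last entrant's third dataset would fall at about 30 June 2023. Month 12 for a woman enrolled at diagnosis on the last day would fall on 31 December 2023.

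**The case against.** The strongest reply is that the calendar date is a backstop and the hard stop is a deliberate choice. Recruitment closes earlier if ten evaluable women are reached, and 4.5 openly accepts a shortfall. The document reports no accrual, and 21 January 2022 is a version date rather than a recruitment start. Whether any woman is affected is therefore unknown. This stands, and the point is conditional on accrual still being open. It does not remove the shared date, and the January 2022 text expressly allows recruitment through that year.

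A reader might go further than the documents allow in three ways.

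- **That women enrolled at diagnosis in 2022 would have no outcome.** Section 6.2 accepts a colposcopy outcome, the Synopsis allows follow-up of six months, and colposcopy is done at every visit. Entrants up to June would have three or four datasets and an outcome. What they lose is the 12-month histology.
- **That none of those women would be counted.** This follows only if full duration in 6.1 means 12 months. The Synopsis range and the three-dataset rule in 4.5 point the other way, so this is an ambiguity to settle.
- **That the loss biases the comparison.** A calendar cut is administrative censoring. Nothing in the protocol links entry date to regression or progression.

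The exact cut-off also depends on the assumed visit window, as shown above. If a patch taken earlier under the Cell Lift study counted as a dataset, the June limit would ease, but the protocol does not say that it does.

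**Conclusion.** The point holds in a limited form. If accrual is open, entry after 30 June 2022 cannot yield an evaluable participant on any route, or after about 14 July with a two-week tolerance. This covers six months of permitted recruitment on the nominal schedule. No woman enrolled at diagnosis on or after the version date can have her planned 12-month histology captured. Pathway entrants can, if they enter by 31 March (month-3 entry) or 30 June 2022 (month-6 entry). Within 4.5, the fixed stop contradicts the follow-up and last-visit sentences for any woman still active at the end of 2022.

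These conclusions assume three-monthly visits as scheduled, one dataset per study visit, and no credit for samples taken before entry. The number of women affected cannot be derived from the protocol.

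**What to change.** In section 4.5, set last entry at 30 June 2022 for all routes, or earlier if ten evaluable women are reached. Then choose one of two options.

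1. **Keep data capture to the end of 2022.** Amend the sentences on the last follow-up visit and on still-active women to say that follow-up is captured only to that date. State that women enrolled at diagnosis in 2022 will contribute a colposcopy outcome and not 12-month histology.
2. **Replace the end-2022 data stop** with capture until the last enrolled woman's 12-month visit. With last entry on 30 June 2022, this is about 30 June 2023 at the latest.

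Under either option, define full duration in 6.1 so that it agrees with the three-dataset rule in 4.5.

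Both options need a protocol amendment. The last-entry date costs almost nothing, because on the nominal schedule it turns away only women who could not become evaluable. With a two-week tolerance it also gives up about two weeks of usable entry. Option 1 accepts the loss of 12-month histology for 2022 diagnosis-route entrants. Option 2 keeps it at the price of up to about six more months of data capture.

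A separate cut-off of 31 December 2021 for the diagnosis route is not advised. It precedes this version and would exclude women who can be evaluable under 4.5.
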